9.2.5.4 Vaccinated Case-Coverage Design

For the vaccinated case-coverage analysis, exposure and comparison windows will be defined using the same guidance and considerations as the CCO design, and cases that were vaccinated in either window will be informative to analysis. For each case, the observed odds of vaccination within the exposure window will be estimated and compared with an expected odds of vaccination inside the exposure window, which will be estimated in an external reference population. Data to estimate the expected odds of vaccination may come from population-based registers or surveys, or other secondary data sources that reflect temporal patterns in vaccination among the target population in the catchment areas for cases.

To calculate the expected odds of vaccination in the exposure window for each case, strata comprising all persons in the reference population who are similar to the case with respect to confounder status (e.g., age, sex, and risk factors) on the day of outcome onset will be created. Then the odds of vaccination in the same calendar period equating to the case's exposure window will be computed in the reference population. Reference population individuals in the stratum had to have received the same vaccine during the same calendar periods equating to the exposure or comparison windows before the onset of the case onset date and had to belong to the same groups as the case with regard to predefined confounding factors (e.g., age, sex, high-risk conditions). These predefined confounding factors will be selected on the basis that temporal patterns in vaccination are likely to be different across different levels of the confounder. Of note, this design requires information on vaccination in the reference population by risk factors and calendar date of vaccination. It is anticipated that these data will not be available for the catchment areas of most hospital sites.

Further Considerations for all Designs

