9.6.2 Measures of Association

If the SCRI is used, conditional Poisson regression (conditioned on the individual) will be used to estimate incidence rate ratios and 95% confidence intervals for each outcome, with logarithm of time in each interval as the offset. If the CCO is used, conditional logistic regression (conditioned on the individual) will be used to estimate odds ratios and 95% confidence intervals for each outcome.

For the SCRI and CCO, time-varying confounders will be adjusted for in regression models. If applicable, in the SCRI, age and calendar time may be categorised into several categories, or treated as polynomial functions, with or without the use of splines in regression models. Both unadjusted and adjusted incidence rate ratios, by site and pooled across all sites, will be reported.

If the vaccinated case-coverage design is used, a logistic regression model will be fit for each AESI under study using separate summarised data sets. The data set for each AESI under study will have one record per risk set (i.e., case), with the outcome indicating whether vaccination occurred in the case's exposure or comparison window. The logarithm of the expected odds (i.e., logit) of vaccination inside the exposure window will be entered into the model as an offset term. For each case, this expected probability of vaccination inside the exposure window will be obtained from the reference population, as described in Annex 3. The model will include only an intercept with no covariate, with the following general form.

$$\text{Logit}(p_1) = \text{logit}(p_0) + \beta_0,$$

where p_1 is the observed probability of vaccination inside the exposure window among cases, p_0 is the expected probability of vaccination inside the exposure window among cases (based on vaccination data in the reference population), β_0 is the intercept; by exponentiating this coefficient, one obtains an odds ratio describing the association between vaccination and the outcome of interest occurring inside the risk interval.

Of note, the logistic regression model drops all cases for whom the expected probability of vaccination inside the exposure window is 0 or 1 (i.e., either everyone or no one is vaccinated inside the risk interval amongst the reference population), as these cases are noninformative.

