9.8 Limitations of the Research Methods

The study is subject to limitations due to both the study design and use of clinical data and other data not collected for research purposes. The major limitation of self-controlled designs and their variants is that they are only suited to study outcomes with a short induction period and an abrupt onset. These designs are not appropriate for assessing outcomes with gradual onset or a long induction period.

Other limitations of self-controlled designs and their variants (including the vaccinated case-coverage design as proposed in this template) include the possibility that incorrectly specifying the risk window will lead to biased incidence rate ratio/odds ratio estimates. If the risk window is not well characterised based on prior data or studies, sensitivity analyses with alternative risk interval definitions should be undertaken. Other

study design approaches that are less susceptible to this source of bias (for example, a cohort design with historical comparators or a traditional cohort design) could also be used as complimentary approaches, as appropriate. Another limitation of the SCRI and CCO is that they are susceptible to bias due to time-varying confounders such as infections. While attempts to collect and adjust for time-varying confounders will be made, not all data sources will have information on them. A major limitation of the CCO is that it should not be used if there are temporal trends in exposure. While the vaccinated case-coverage design addresses potential bias due to time trends in exposure, it assumes that the temporal trends in exposure are the same in cases as they are in the reference population. Another limitation is that it requires information on the number of persons vaccinated on a daily basis, stratified by subgroups of important confounders; it is anticipated that this information will not be available for populations of interest for the catchment areas of all hospital sites. Finally, the vaccinated case-coverage design is that it may have less statistical power than the CCO and the SCRI designs, as cases for whom nearly everyone or no one is vaccinated during the risk window are uninformative for the analysis.

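### Section 9.6.2 calls every case with an estimated reference proportion of 0 or 1 noninformative; if the reference omits the case and strata are small, the odds ratio is biased in the direction of the uptake trend

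*Protocol*

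**What the plan says.** Section 9.6.2 fits an intercept-only logistic model with one record per case. The outcome is which of the two windows the case was vaccinated in. On the offset, the section says: "The logarithm of the expected odds (i.e., logit) of vaccination inside the exposure window will be entered into the model as an offset term", and "this expected probability of vaccination inside the exposure window will be obtained from the reference population". It then states that "the logistic regression model drops all cases for whom the expected probability of vaccination inside the exposure window is 0 or 1"; the justification given for this removal is "as these cases are noninformative".

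Section 9.2.5.4 describes where that probability comes from. The expected odds are a quantity "which will be estimated in an external reference population", using "strata comprising all persons in the reference population who are similar to the case with respect to confounder status" (age, sex and risk factors are the examples). The stratum is then narrowed: "Reference population individuals in the stratum had to have received the same vaccine during the same calendar periods" as the case's exposure or comparison window. Registers, surveys and other secondary sources are all allowed, and Annex 3 also allows representative samples. No minimum stratum size is given, and nothing says whether the case is among the persons counted.

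Section 9.8 treats the dropping purely as a matter of power: "cases for whom nearly everyone or no one is vaccinated during the risk window are uninformative for the analysis". Table 2 makes this design the primary analysis when vaccination trends are observed and suitable reference data exist.

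**The concern.** A finite stratum can show a proportion of exactly 1 although the true probability is, say, 0.9. If the case is not one of the persons counted and was vaccinated in the comparison window, case and stratum disagree. That disagreement is evidence against an association, and the rule discards it.

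Under rising uptake, strata that reach 1 are removed often and strata that reach 0 almost never. The retained reference proportions are therefore pulled toward 0.5 while the cases are not. The offset is too small, and the intercept, which is the reported log odds ratio, absorbs part of the trend. Falling uptake does the reverse. The design exists to remove such trends, so leftover trend bias matters more than lost precision: it could suggest harm where there is none, or hide real harm.

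**Working it through.** The protocol states no numerical property for this design, so there is no figure of its own to reproduce.

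**Inputs.** From sections 9.2.5.4 and 9.6.2: the offset model, the drop rule and a reference external to the cases. Assumed, because the protocol is silent: m reference vaccinees per stratum (5 to 50), true probability p0 of vaccination in the exposure window, the same p0 for every case, and a case not counted in the reference. For scale, the example windows in section 9.2.5.3 (days 1–21 and 50–70 before the event) are 49 days apart. Uptake doubling every 28 days gives odds of 2^(49/28) = 3.36, so p0 = 0.77. Doubling every 14 days gives 2^(49/14) = 11.3, so p0 = 0.92.

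**Formula.** The number of reference vaccinees in the exposure window is X ~ Bin(m, p0). The case falls in that window with probability p1 = OR·p0/(1 − p0 + OR·p0). Strata with X = 0 or X = m are dropped. The large-sample estimate exp(b) solves

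Σ over k = 1,…,m−1 of P(X = k)·[p1 − expit(log(k/(m−k)) + b)] = 0.

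**The mechanism by hand, p0 = 0.9, m = 10, true OR 1.** P(X = 10) = 0.9^10 = 0.349; P(X = 0) is negligible. The mean retained proportion is (0.9 − 0.349)/(1 − 0.349) = 0.846. The cases' odds are 0.9/0.1 = 9, while the retained reference odds are about 0.846/0.154 = 5.5. The ratio is about 1.64; the exact solution is 1.66.

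**Exact results, true OR 1.**

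| p0 | m=5 | m=10 | m=20 | m=50 |
|---|---|---|---|---|
| 0.1 | 0.33 | 0.60 | 0.86 | 0.994 |
| 0.5 | 1.00 | 1.00 | 1.00 | 1.00 |
| 0.8 | 1.77 | 1.17 | 1.02 | 1.00 |
| 0.9 | 3.04 | 1.66 | 1.16 | 1.006 |

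At m = 30 the values are 1.002 (p0 0.8) and 1.05 (p0 0.9). A more extreme p0 of 0.95 gives 1.62 at m = 20 and 1.09 at m = 50. In a simulation with 100 cases and p0 = 0.9, type I error at a nominal 5% was 60%, 18% and 5% for m = 5, 10 and 20.

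**True OR 2 with falling uptake (p0 0.1).** The estimate is 0.68, 1.24 and 1.77 for m = 5, 10 and 20.

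**Case counted once in its stratum.** Let k′ be the number in the exposure window among the m + 1 persons. Given k′, the case is in that window with probability OR·k′/(OR·k′ + m + 1 − k′). This is the model of section 9.6.2 with offset log(k′/(m + 1 − k′)), and it is the conditional likelihood of the matched set. The same enumeration returns 1.000 and 2.000 at every m and p0 tried.

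**The case against.** The strongest reply is that the rule may already be right. Cases are vaccinated residents of the catchment areas, and a population-based register of those areas would contain them. The protocol's external may mean only outside the hospital case series. If the case is in its own stratum, a proportion of 0 or 1 means that it agrees with everyone else, and it is indeed noninformative. This stands: the fault is conditional on a source that omits the case, and a fix that always adds the case would count it twice in such a register. Double counting attenuates a true OR of 2 to 1.85, 1.91 and 1.95 (m = 5, 10, 20 at p0 0.8), though it leaves the null untouched.

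A reader might infer that the rule throws away mostly informative cases. It does not. At p0 = 0.9 and true OR 1 it drops 59%, 35% and 12% of cases for m = 5, 10 and 20. The matched-set analysis still drops 0.9^(m+1), that is 53%, 31% and 11%. Deletion also depends on the reference stratum, not on the case's own window.

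Nor is dropping the whole cause. At true OR 2, p0 0.5 and m = 10 only 0.2% of cases are dropped, yet the estimate is 2.15. That is error from treating an estimated offset as known. Adding 0.5 to the cells, which keeps every case, still gives 1.45 under the null at p0 = 0.9 and m = 10.

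Small strata are not established either. Catchment area describes what the source should represent and is not a listed matching factor, so register strata may be large. An infinite offset cannot be fitted, so some handling is needed, and minimum stratum sizes or pooling could be left to an analysis plan. The stated reason for dropping, however, is in the protocol itself and is not generally true.

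**Conclusion.** The point holds in conditional form. Section 9.6.2 treats an estimated proportion as known and gives a reason for dropping cases that is valid only when the case is in its own stratum or the true probability is 0 or 1. Where the source omits the case and strata are below roughly 20 to 30 vaccinees (more if p0 is extreme), the result is bias along the uptake trend, whereas section 9.8 discloses only a loss of power.

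The size rests on assumed m and on a p0 shared by all cases. The bias shrinks when trends are mixed: probabilities of 0.9, 0.7, 0.5 and 0.3 with weights 0.5, 0.25, 0.15 and 0.1 give null values of 1.36, 1.15 and 1.04 for m = 5, 10 and 20. It cancels if rising and falling periods balance exactly. The documents do not support the conclusion that this design will give a false odds ratio whenever uptake is changing, because they give no stratum sizes and allow complete registers. It is still worth correcting, because this is a template whose wording may be carried unchanged into derived studies, and the design is primary in one of the Table 2 scenarios.

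**What to change.** In section 9.6.2, replace the drop rule with wording to this effect: *Each case is counted exactly once in its own stratum when the expected odds are computed. It is added if the reference source omits it, and not added again if the source already contains it. This is equivalent to conditional logistic regression of the case against its reference vaccinees. Only strata in which the case and all reference vaccinees fall in the same window are noninformative.* Amend the sentence in section 9.8 on uninformative cases to match, and say in section 9.2.5.4 whether the reference counts include the case.

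The change needs only the stratum counts that the design already requires. The real cost is that each site must establish whether its reference source contains the case. Where strata are large there is no material effect on the estimate.

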9.6.3 Data Integration

Results will be presented separately for each data source and pooled across data sources.

The method for pooling of results will depend on the data-sharing policies of each of the participating hospitals. If all sites are able to share individual-level data or aggregate data needed for the analysis (e.g., case counts by vaccination interval and covariate status), local investigators will transfer their site’s individual-level data to the study coordinating centre to contribute to an analysis with one-stage pooling.

If some or all sites do not allow the necessary patient-level or aggregate data to be shared, then data analysis could be performed by data custodians at their sites behind firewalls. Counts and coefficients would be shared with the study coordinating centre, and overall results would be summarised using meta-analytic techniques.

Alternatively, if some institutions are able to share the necessary patient-level or aggregate data and others are not, a hybrid approach for pooling of data could be taken [9]. Depending on data-sharing restrictions, local investigators would either transfer aggregated data to the study coordinating centre for further analysis and pooling, or they would run the same analyses locally and transfer coefficients and counts to the coordinating centre. Both the pooled odds ratios/incidence rate ratios and individual odds ratios/incidence rate ratios from sites would then be summarised in a meta-analytic technique.

9.6.4 Subgroup Analysis

If relevant to specific adverse events, the presence of effect modification by relevant variables (dose number, age at vaccination, specific comorbidities, concomitant vaccinations) will be assessed by adding an interaction term between vaccination and the effect modifier of interest to regression models for the CCO and SCRI designs. Effect modification will be assessed in the vaccinated case-coverage design by adding the potential effect modifier as a covariate to the regression model.

Subgroup analysis will be performed by strata of effect modifiers of interest as relevant. For the vaccinated case-coverage design, subgroup analysis will require that the at-risk-stratum for calculating the expected odds of vaccination be redefined based on the different subgroups.

[The study investigator(s) should describe subgroups motivated by the current understanding of the study outcomes in this section.]

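### Section 9.6.4 carries the redefined expected odds over to subgroup analysis but not to the covariate test of effect modification, so in the vaccinated case-coverage design a difference in vaccination timing between doses can appear as effect modification

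*Protocol*

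**What the plan says.** Section 9.6.2 fits a logistic model with an intercept and no covariate to the vaccinated cases: logit(p1) = logit(p0) + β0. On the offset it says: "The logarithm of the expected odds (i.e., logit) of vaccination inside the exposure window will be entered into the model as an offset term".

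Section 9.2.5.4 says who supplies p0. Reference persons "had to have received the same vaccine during the same calendar periods equating to the exposure or comparison windows", and they "had to belong to the same groups as the case with regard to predefined confounding factors (e.g., age, sex, high-risk conditions"; the items in brackets are examples. Neither this section nor the description in Annex 3 names dose number or concomitant vaccination as a stratum factor.

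Section 9.6.4 lists the modifiers as "dose number, age at vaccination, specific comorbidities, concomitant vaccinations". Its first paragraph ends by saying that this design will test for effect modification "by adding the potential effect modifier as a covariate to the regression model". That sentence does not mention the offset. The next paragraph, on stratified results, says that for this design "subgroup analysis will require that the at-risk-stratum for calculating the expected odds of vaccination be redefined based on the different subgroups".

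Dose number is among the secondary objectives in section 8, and the effect-modifier part of section 9.2.5.5 commits to assessing it for a multidose vaccine.

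**The concern.** In this model the offset does the work that a control group does elsewhere: it says how the cases' vaccinations would fall between the two windows if the vaccine had no effect. If two levels of a modifier have different vaccination calendars, each level needs its own p0. If both share a pooled p0, the modifier's coefficient picks up the difference in calendars.

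Second doses follow first doses, so their calendar is shifted. Table 2 makes this design primary when temporal trends in vaccination are observed, and that is the setting in which a shifted calendar usually changes p0. A report could therefore attribute a risk difference to one dose when only timing differs. The covariate test and the subgroup analysis, run on the same cases, could also give different answers to the same question.

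**Working it through.** The protocol states no figure for this analysis (Table 3 covers SCRI sample size only), so there is nothing to reproduce.

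**Algebra.** Take one reference stratum and a binary modifier M. Let p0(0) and p0(1) be the expected probabilities at the two levels, p0(pool) their pooled value, and OR(0), OR(1) the true odds ratios. Among cases, logit p1(M) = logit p0(M) + log OR(M). Fitting logit p1 = logit p0(pool) + b0 + b1·M gives

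b1 = [log OR(1) − log OR(0)] + [logit p0(1) − logit p0(0)].

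The second bracket is the error. The pooled value cancels from b1 and goes into b0. Over many strata the error is a weighted average of such differences.

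**Size when both true odds ratios are 1.** The spurious ratio is the ratio of the two expected odds:
- p0 of 0.45 and 0.55: (0.55/0.45) ÷ (0.45/0.55) = 1.49
- p0 of 0.40 and 0.60: (0.60/0.40) ÷ (0.40/0.60) = 2.25
- p0 of 0.30 and 0.70: (0.70/0.30) ÷ (0.30/0.70) = 5.44

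**Dose example.** From the CCO example in section 9.2.5.3, which section 9.2.5.4 adopts as guidance: exposure window 1 to 21 days and comparison window 50 to 70 days before the event, doses 28 days apart. The windows are at least 50 − 21 = 29 days apart, so nobody has a dose in each and every informative case has one dose number. Roll-out curves and event dates are assumptions; the protocol gives none. The second-dose curve is the first-dose curve shifted by 28 days. A binomial model with intercept, dose indicator and dose-pooled offset was fitted to expected counts with a true odds ratio of 1 for both doses.

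| Assumed first-dose roll-out | Event days | Dose 1 OR | Spurious ratio, dose 2 / dose 1 |
|---|---|---|---|
| Exponential growth or decline, 3% per day | 100–200 | 1.00 | 1.00 |
| Flat | 80–200 | 0.96 | 1.10 |
| Flat, early events only | 80–100 | 0.77 | 1.83 |
| Linear ramp | 80–200 | 0.91 | 1.24 |
| Bell, peak day 120, SD 60 | 75–259 | 0.82 | 1.48 |
| Bell, peak day 120, SD 40 | 75–259 | 0.68 | 2.13 |
| Bell, peak day 120, SD 25 | 75–259 | 0.45 | 4.94 |
| Bell, peak day 90, SD 30 | 80–200 | 0.54 | 3.46 |

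The SD 60 figure is 1.44 if the curve is not cut off before day 1. With SD 25 the dose 2 odds ratio is 2.22.

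The exponential rows show no error because a 28-day shift multiplies both windows by the same factor. The flat rows show some because, early on, the second-dose comparison window reaches back before second doses began.

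One day shows the mechanism. In the last row, at day 130, p0 is 0.44 for dose 1, 0.77 for dose 2 and 0.60 pooled.

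**False positives.** For the last row, 1,000 simulated data sets at two-sided 0.05 gave a rejection rate for the dose term of 61% with 69 cases and 97% with 200.

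**With p0 calculated within dose.** The ratio is 1.00 in every dose scenario refitted this way (all rows except the three with the peak at day 120, where the algebra gives the same). Rejection rates are 4.7% (69 cases) and 5.2% (200 cases). The intercept-only odds ratio is 1.00 under the pooled offset as well, so the main analysis is not distorted and also gives no warning.

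**The case against.** - **The protocol does not say the offset stays pooled.** A reader might infer that 9.6.4 prescribes an unchanged offset. It does not; the covariate sentence is silent. This stands. But the redefinition rule in the same section is limited to subgroup analysis, and the only other description of p0 leaves dose out, so someone following the text would pool over dose.
- **The general rule for stratum factors may cover it.** Section 9.2.5.4 chooses factors because vaccination timing differs across their levels, which is the condition for the error. An investigator could extend this to dose. The rule is written for confounders, however, and does not name dose.
- **Not every listed modifier is affected.** A reader might infer that age and comorbidity tests fail too. Where age or a high-risk condition is already a stratum factor, at the grouping used for the test, the offset is specific to the modifier and no such error arises. This stands in full.
- **Dose does not always distort.** A reader might infer that any change in uptake biases the dose test. The exponential case disproves it, and every roll-out shape here is assumed.
- **Reach is limited.** The analysis is secondary and runs only where relevant to the event, and section 9.2.5.4 expects suitable reference data to be missing for most sites. Table 2 pairs this design with the SCRI, for which section 9.2.5.2 evaluates doses separately, so a dose finding could be cross-checked. That check is lost where section 9.2.5.3 resorts to a person-level analysis combining the doses' risk intervals.
- **It is a template, and offset construction could be left to the SAP.** Missing detail alone would be no finding. Here the protocol fixes the model and the test, and states the offset rule for only one of two parallel analyses.

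**Conclusion.** The point holds for modifiers outside the reference strata: chiefly dose number, also concomitant vaccination and any comorbidity not matched on. As written, the covariate test in 9.6.4 adds the difference in logit(p0) between levels to the effect it is meant to estimate.

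For dose, under the protocol's example windows, a 28-day gap and no true effect, the spurious ratio of odds ratios runs from 1.0 (exponential) through about 1.1 (flat, events spread over the roll-out) and 1.2 (linear ramp) to about 1.4 to 4.9 (bell-shaped, SD 60 to 25 days). The algebra needs no assumption about roll-out; the size does. The false-positive rates belong to one bell-shaped curve and should not be read as general. The overall odds ratio for this design is not affected. This should be corrected before the template is used, but it does not undermine the primary analysis.

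**What to change.** Add to section 9.6.4:

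> For the vaccinated case-coverage design, the expected odds used as the offset will be calculated within levels of the effect modifier (for dose number, from dose-specific vaccination dates in the reference population), both for the covariate test and for the subgroup analysis. Where the reference data cannot be split by a modifier, that modifier will not be tested with this design.

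The text change is one sentence plus its restriction, and it reuses strata that the plan already requires for subgroups. With a categorical modifier, the covariate model and the subgroup analyses then give the same level-specific odds ratios.

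There are two costs. Some modifiers become untestable at sites whose reference data lack them. Finer strata will also more often give a p0 of 0 or 1, for example for second doses early in the roll-out, and section 9.6.2 drops those cases. The number dropped should be reported by modifier level.
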